10.1 Definitions

The following definitions will be used in the assessment of safety:

Adverse Event (AE) is any untoward or unfavorable medical occurrence in a human subject, including any abnormal sign (for example, abnormal physical exam or laboratory finding), symptom, or disease, temporally associated with the subject's participation in the research, whether or not considered related to the subject's participation in the research. Participation in the research does not include the time between Phase I and Phase II of the study. Subjects will not be monitored for adverse events in the time between Phase I and Phase II as there are no study activities during this time period.

Serious Adverse Event (SAE) is any adverse event that

- (1) results in death;
- (2) is life-threatening;
- (3) results in inpatient hospitalization or prolongation of existing hospitalization;
- (4) results in a persistent or significant disability/incapacity;
- (5) results in a congenital anomaly/birth defect; or
- (6) based upon appropriate medical judgment, may jeopardize the subject's health and may require medical or surgical intervention to prevent one of the other outcomes listed in this definition (examples of such events include allergic bronchospasm requiring intensive treatment in the emergency room or at home, blood dyscrasias or convulsions that do not result in inpatient hospitalization, or the development of drug dependency or drug abuse).

Life-threatening means that the event places the subject at immediate risk of death from the event as it occurred.

Unanticipated Problem is defined as an event, experience or outcome that meets **all three** of the following criteria:

- is unexpected; AND
- is related or possibly related to participation in the research; AND

Calibration Study of a Wearable Noninvasive Blood Alcohol Monitor

Final V1.8 4.24.19

- suggests that the research places subjects or others at a greater risk of harm (including physical, psychological, economic, or social harm) than was previously known or recognized.

Possibly related means there is a reasonable possibility that the incident, experience, or outcome may have been caused by the procedures involved in the research

Unexpected means the nature, severity, or frequency of the event is not consistent with either:

- the known or foreseeable risk of adverse events associated with the procedures involved in the research that are described in (a) the protocol-related documents, such as the IRB-approved research protocol, any applicable investigator brochure, and the current IRB-approved informed consent document, and (b) other relevant sources of information, such as product labeling and package inserts; or
- the expected natural progression of any underlying disease, disorder, or condition of the subject(s) experiencing the adverse event and the subject's predisposing risk factor profile for the adverse event.

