If a subject completes Phase I and is unable to complete Phase II for any reason, replacement subjects will be recruited to complete Phase I and II consecutively. It is estimated that 36 subjects will be consented to yield 12 subjects that will complete Phase I and 9 subjects that will complete Phase II. Based on past experience with subject attrition, it is estimated that 33% of the Phase I subjects will be replaced at the time of phase II. Given the sample size requirements for this study are 9 subjects to complete both trials, the total sample size is estimated to be 12 subjects taking into account the possibility that three subjects will be lost to follow-up between trials one and two. If subjects are lost, when these subjects are replaced they will complete both the calibration session and validation session over the period of approximately 60 days.

Subject compensation

Subjects will be compensated up to \$340 for completion of all study activities. In addition to reimbursements for each study visit, subjects who complete all study visits will receive a completion bonus at the end of the study. If at any time subjects are discontinued from the study during a visit, subjects will be paid a portion of the payment based on time completed (e.g., 1

Calibration Study of a Wearable Noninvasive Blood Alcohol Monitor

Final V1.8 4.24.19

hour completed of two-hour visit = 1/2 of payment). Note there is an exclusion for payment due to UDS+ at the baseline.

Subjects will receive the following reimbursements:

Baseline assessment	\$40
Phase I BAL Calibration session	\$100
Phase II eligibility determination session	\$40
Phase II BAL validation session	\$100
Completion Bonus	\$60

10 Assessment of Safety and Data Safety Monitoring Plan (DSMP)

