10.2 Safety Review

Both the risks listed in Section 6.1 and unknown risks will be monitored as follows:

Adverse events will be monitored from the time of study consent through the end of the first drinking session. Adverse events will not be monitored in the estimated 9 months between drinking session 1 and drinking session 2 as there are no study activities in this period. Adverse event monitoring will resume when the subject returns to complete assessment prior to the second drinking session, and it will continue until the subject has completed the study.

Adverse events will be monitored by medical staff using the "adverse events" CRF. Adverse events will be assessed on the alcohol self-administration day. If a subject has an ongoing SAE or unanticipated problem at the time that the subject completes all study procedures, Adverse Event assessment will continue until satisfactory resolution (either resolved or stabilized and is not expected to resolve in the near term) of the event or problem.

For each recorded AE or SAE, the study MD staff or study nurse will assess expectedness based on the known risks of study participation. The study MD staff or study nurse will also assess severity based on the following criteria:

Mild: An event that is usually transient, requiring no special treatment, and does not generally interfere with the subject's daily activities.

Moderate: An event that interferes with usual activities of daily living, causing discomfort but poses no significant or permanent risk of harm to the subject. The event is usually ameliorated with additional specific therapeutic intervention.

Severe: An event that interrupts usual activities of daily living or significantly affects clinical status. The event poses a significant risk of harm to the

Calibration Study of a Wearable Noninvasive Blood Alcohol Monitor

Final V1.8 4.24.19

Mild:	An event that is usually transient, requiring no special treatment, and does not generally interfere with the subject's daily activities.
	subject and hospitalization may be required, and typically requires intensive therapeutic intervention.
Life-threatening	An event that puts the subject into imminent risk of death without intervention.

Study staff will assess whether AEs and SAEs are unexpected:

Unexpected means the nature, severity, or frequency of the event is not consistent with either:

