10.3 Stopping Rules

There are no interim analyses planned that would allow for a determination of futility or overwhelming benefit. Study enrollment will be suspended under the following circumstances:

Calibration Study of a Wearable Noninvasive Blood Alcohol Monitor

Final V1.8 4.24.19

1. Serious Adverse Events. Study enrollment will be suspended in the event of a single serious adverse event that is determined to be unexpected and at least possibly related (i.e. it is an Unanticipated Problem). If suspended, study recruitment will not continue until a determination has been made about whether the known risks of participation have changed and the BU Medical Campus/Boston Medical Center IRB has made a finding that the risk/benefit ratio remains favorable given the possible newly identified risk.
2. Risk of intoxication. Subject recruitment will also be suspended if more than one subject of the first ten subjects enrolled is discontinued by the investigator due to intoxication during the alcohol self administration trial. Due to differences in alcohol tolerance, BAL is not a reliable measure of subjects potentially posing a safety risk. Medical staff will make a subjective determination of risk based on the subject's behavior. After 10 subjects have been enrolled, the trial will be suspended if there are more than 10% of subjects whose participation has been halted by the study team due to concerns about physical safety because of intoxication during the alcohol self-administration trial. If suspended for this reason, the study team will consider design changes to reduce the likelihood of this as a potential risk to study subjects. Recruitment would resume when the BU Medical Campus/Boston Medical Center IRB has made a determination that proposed changes to the study design have an acceptable risk/benefit ratio.

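### Adverse-event capture ends with drinking session 1 and between-phase events are defined out, so a serious event soon after discharge is not recorded and reaches the suspension rule only if the site happens to hear of it

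*Combined protocol and SAP*

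**What the plan says.** Section 10.1 defines an AE by its association in time with taking part in the research, and defines an SAE as an AE meeting a seriousness criterion. It then states: "Participation in the research does not include the time between Phase I and Phase II of the study".

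Section 10.2 sets the monitoring window: "Adverse events will be monitored from the time of study consent through the end of the first drinking session". It continues: "Adverse events will not be monitored in the estimated 9 months between drinking session 1 and drinking session 2", giving the absence of study activities as the reason. Capture reopens later: "Adverse event monitoring will resume when the subject returns to complete assessment prior to the second drinking session". It then runs until the subject has completed the study. Appendix A lists AEs at all four visits, and the session 2 visit is the last.

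Section 10.2 provides follow-up to satisfactory resolution for an SAE or unanticipated problem that is ongoing "at the time that the subject completes all study procedures". It mentions no other point at which such follow-up begins.

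Section 10.3 suspends enrollment "in the event of a single serious adverse event that is determined to be unexpected" and at least possibly related, and equates that event with an Unanticipated Problem. Section 10.1 defines an Unanticipated Problem more broadly than an AE, without limiting it to the monitoring window. The reporting times in Section 10.4 run from when the investigator learns of the event.

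Section 9 allows for the possibility that "three subjects will be lost to follow-up between trials one and two", out of 12.

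**The concern.** The reason given for the unmonitored interval suits the months between sessions. It does not suit the hours or days just after the study has given alcohol, when a delayed, dosing-related event is most plausible. As written, the excluded interval starts as soon as session 1 ends.

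Two things are at stake. First, the safety count, and the AE summary sent to the IRB at continuing review, would omit such an event by rule rather than by accident. Second, the first suspension rule acts on a single event, so one missed event can decide whether it operates. Subjects who stop early are the least likely to have a later visit at which an event could come to light.

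**Working it through.** **Tracing an event through the text**

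1. An AE requires association in time with participation (10.1).
2. Time between the phases is not participation (10.1), and monitoring is off from the end of session 1 (10.2).
3. An SAE is a kind of AE (10.1). An event that starts in the gap is therefore not an SAE, even if the subject reports it at the Phase II eligibility visit.
4. The suspension rule is worded for an SAE (10.3) but equated with an Unanticipated Problem, which is not limited to the window (10.1, 10.4). For the same gap event, one wording excludes it and the other admits it.

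| Event | AE/SAE as written? | Route to the 10.3 rule | Follow-up to resolution |
|---|---|---|---|
| Starts in session 1, ongoing at its end | Yes | Yes, on assessment | None stated at that point |
| Starts after discharge from session 1 | No | Only if the site hears of it and treats it as an Unanticipated Problem | None stated at that point |
| Starts in a session, subject then halted, withdrawn or lost | Yes | Yes, on assessment | None stated |
| Starts in session 2, ongoing at study completion | Yes | Yes, on assessment | Yes |
| Starts after discharge from session 2 | Monitoring has ended; no contact planned | Only if the site hears of it | None stated |

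**Size, from Section 9**

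- The plan's total reproduces at 25% loss: 9 / (1 − 0.25) = 12, with 3 of 12 not returning.
- Section 9 also gives a 33% replacement rate: 0.33 × 12 = 3.96, about 4. That rate would need 9 / (1 − 0.33) = 13.4, or 14 subjects, so the two rates do not agree. The range for non-returners is 3 to 4 of 12.
- Sessions before any replacements: 12 + 9 = 21. Those with no later scheduled visit: 3 (Phase I non-returners) + 9 (Phase II) = 12 of 21, or 57%.
- The unmonitored interval after session 1 is an estimated 9 months (10.2). Replacement subjects complete both sessions in about 60 days (Section 9).

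**Illustration only.** The documents give no rate of events after discharge. If each of 12 subjects had an independent risk p of one, the chance of at least one event is 1 − (1 − p)^12:

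| Assumed p | Chance of at least one in 12 |
|---|---|
| 1% | 11.4% |
| 2% | 21.5% |
| 5% | 46.0% |
| 10% | 71.8% |

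**Where the excluded interval begins.** This depends on discharge, and the discharge passages conflict. Section 5 (Calibration Phase I), Section 6.1 (Subject release) and Section 9 (Alcohol Administration) work with 0.04 g/dL. Section 9 (Observation) says monitoring continues to 0.0 g/dL.

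**The case against.** The unmonitored gap is an explicit choice with a stated reason, and the exposure is modest: two sessions aimed at 0.05 g/dL in regular drinkers. The plan also has real protections: a five-hour observation in Phase I, an expectation of 0.00 g/dL when that session ends, retention of impaired subjects, nursing supervision and a transport plan that excludes driving. These stand and may lower the risk, but none of them detects an event after discharge.

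Several stronger readings are tempting, and the documents do not support them:

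- A reader might infer that an SAE ongoing at the end of session 1 goes uncounted. It does not. It started inside the window, and the 10.3 threshold is one event, whatever its later course. Only its outcome follow-up is unwritten.
- A reader might infer that an event after discharge can never trigger suspension. If the site hears of it, the Unanticipated Problem definition and reporting clock are open to it.
- A reader might infer that the plan expressly restricts follow-up to completers. It does not; the restriction comes from silence about everyone else.
- A reader might infer that subjects are simply released at 0.04 g/dL. The passages conflict, so that cannot be assumed.
- Section 10.2 also says AEs are assessed on the alcohol self-administration day. This could be read as extending capture slightly past the session, but it sets no contact after discharge and does not undo the exclusion in 10.1.

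It is also fair that 10.3 requires an unexpected event. Some consequences of drinking, perhaps a fall, might be judged expected and would not trigger the rule even if recorded. That limits the effect on suspension, not the effect on the AE and SAE count.

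**Conclusion.** The concern holds in a bounded form. Following the plan as written leaves a dosing-related serious event soon after discharge from session 1 out of the AE and SAE records. Its path to suspension then depends on the site happening to learn of it, and on which of two conflicting wordings staff apply. This affects all 12 planned Phase I subjects. Follow-up of an ongoing SAE is unwritten at the end of session 1 and for those who leave early, including the 3 to 4 of 12 expected not to return. New events after session 2 also have no planned ascertainment.

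The counting of SAEs that start during a session, the intoxication-based suspension rule and the primary correlation outcome are unaffected. The conclusion rests on the text of Sections 10.1 to 10.4. It does not depend on any event rate, and the illustrative percentages say nothing about how likely such an event is.

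**What to change.** 1. In 10.1 and 10.2, extend participation and the AE window to a fixed period after each drinking session, with the length set by the investigator. State that an event starting in that window is an AE (or SAE) and counts toward 10.3. The rest of the gap can stay unmonitored.
2. Make one brief contact at the close of that window after each session, using the locator and contact forms already collected, and confirm the answer at the Phase II eligibility visit. Asking only at that visit would be too late: it follows completion of Phase I by all subjects, so the rule could not act during the original Phase I dosing.
3. Apply follow-up to resolution to any SAE or unanticipated problem ongoing at the end of each drinking session, at withdrawal or discontinuation, and at study completion. List each point separately. A trigger worded as the earliest of them could remove the follow-up now provided after session 2.
4. Reconcile the SAE and Unanticipated Problem wording across 10.1, 10.3 and 10.4. Reconcile the discharge passages in Sections 5, 6.1 and 9 as well, since discharge fixes where the new window starts.

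The cost is a short amendment, one brief contact per session and a few more minor AEs on record.

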10.2 Safety Review

Both the risks listed in Section 6.1 and unknown risks will be monitored as follows:

Adverse events will be monitored from the time of study consent through the end of the first drinking session. Adverse events will not be monitored in the estimated 9 months between drinking session 1 and drinking session 2 as there are no study activities in this period. Adverse event monitoring will resume when the subject returns to complete assessment prior to the second drinking session, and it will continue until the subject has completed the study.

Adverse events will be monitored by medical staff using the "adverse events" CRF. Adverse events will be assessed on the alcohol self-administration day. If a subject has an ongoing SAE or unanticipated problem at the time that the subject completes all study procedures, Adverse Event assessment will continue until satisfactory resolution (either resolved or stabilized and is not expected to resolve in the near term) of the event or problem.

For each recorded AE or SAE, the study MD staff or study nurse will assess expectedness based on the known risks of study participation. The study MD staff or study nurse will also assess severity based on the following criteria:

Mild: An event that is usually transient, requiring no special treatment, and does not generally interfere with the subject's daily activities.

Moderate: An event that interferes with usual activities of daily living, causing discomfort but poses no significant or permanent risk of harm to the subject. The event is usually ameliorated with additional specific therapeutic intervention.

Severe: An event that interrupts usual activities of daily living or significantly affects clinical status. The event poses a significant risk of harm to the

Calibration Study of a Wearable Noninvasive Blood Alcohol Monitor

Final V1.8 4.24.19

Mild:	An event that is usually transient, requiring no special treatment, and does not generally interfere with the subject's daily activities.
	subject and hospitalization may be required, and typically requires intensive therapeutic intervention.
Life-threatening	An event that puts the subject into imminent risk of death without intervention.

Study staff will assess whether AEs and SAEs are unexpected:

Unexpected means the nature, severity, or frequency of the event is not consistent with either:

- the known or foreseeable risk of adverse events associated with the procedures involved in the research that are described in (a) the protocol-related documents, such as the IRB-approved research protocol, any applicable investigator brochure, and the current IRB-approved informed consent document, and (b) other relevant sources of information, such as product labeling and package inserts; or
- the expected natural progression of any underlying disease, disorder, or condition of the subject(s) experiencing the adverse event and the subject's predisposing risk factor profile for the adverse event.

The study MD staff or study nurse will assess AE/SAE relationship to the study procedures based on the following criteria:

Unrelated:	The temporal sequence of the AE/SAE onset relative to study procedures is not reasonable, or there is another obvious cause of the AE/SAE.
Unlikely:	It is possible that the AE/SAE is related to exposure to study procedures but there is another more likely cause of the AE/SAE.
Possible:	The temporal sequence of the AE/SAE onset relative to study procedures is reasonable, but the AE/SAE could have been due to another equally likely cause.
Probable:	The temporal sequence of the AE/SAE onset relative to administration of the study procedures is reasonable, and the AE/SAE is more likely explained by the study procedures than by any other cause.
Definite	The temporal sequence of the AE/SAE onset relative to administration of study procedures is reasonable, the AE/SAE is more likely explained by the study procedures than by any other cause, and the AE/SAE shows a pattern consistent with previous knowledge of the risks of study procedures.

10.3 Stopping Rules

There are no interim analyses planned that would allow for a determination of futility or overwhelming benefit. Study enrollment will be suspended under the following circumstances:

Calibration Study of a Wearable Noninvasive Blood Alcohol Monitor

Final V1.8 4.24.19

1. Serious Adverse Events. Study enrollment will be suspended in the event of a single serious adverse event that is determined to be unexpected and at least possibly related (i.e. it is an Unanticipated Problem). If suspended, study recruitment will not continue until a determination has been made about whether the known risks of participation have changed and the BU Medical Campus/Boston Medical Center IRB has made a finding that the risk/benefit ratio remains favorable given the possible newly identified risk.
2. Risk of intoxication. Subject recruitment will also be suspended if more than one subject of the first ten subjects enrolled is discontinued by the investigator due to intoxication during the alcohol self administration trial. Due to differences in alcohol tolerance, BAL is not a reliable measure of subjects potentially posing a safety risk. Medical staff will make a subjective determination of risk based on the subject's behavior. After 10 subjects have been enrolled, the trial will be suspended if there are more than 10% of subjects whose participation has been halted by the study team due to concerns about physical safety because of intoxication during the alcohol self-administration trial. If suspended for this reason, the study team will consider design changes to reduce the likelihood of this as a potential risk to study subjects. Recruitment would resume when the BU Medical Campus/Boston Medical Center IRB has made a determination that proposed changes to the study design have an acceptable risk/benefit ratio.

